Effectiveness of a 6-week Hippotherapy Program in Children With Autism Spectrum Disorder

NCT04772898

11/21/2023

All data collection sessions will take place at the HETRA facility in Gretna, Nebraska. A summarized description of all assessments can be found in Figure 1. Pre- and post-HPOT assessments will take place in a comfortable room located next to the barn at the HETRA facility. The HPOT session will take place within the barn facility.

Standing posture data will be collected pre- and post-HPOT sessions. To collect standing posture data, ground reaction forces (GRF) and moments will be recorded (200 Hz) from a portable force platform (Bertec Corp., Columbus, OH). During quiet stance trials, children will stand with their feet comfortably apart on the force platform. Foot positioning will be marked and used for all subsequent trials. During each trial, children will be asked to stand as still as possible for 20 s with their arms at their sides and facing a bare wall. Children will perform 3-5 trials of standing.

Social play will also be conducted pre- and post-HPOT session. The principal investigator, a student, and caregivers will engage in 10-minute semi-structured play interactions with the child. We will provide board games, building blocks, books, and similar age-appropriate toys depending upon the age of the child. This session will be videotaped for subsequent analysis of targeted social behaviors. At the end of this session, we will also assess the caregiver's perception of the behavior of their child. This survey examines the alertness, emotional reaction, level of interest and attention, comfort level around strangers, level of activity, overall level of communication, and play behavior of the child. The response required from the parents is a three-point scale that assesses/evaluates at *less*, *typical*, or *more/greater* in each behavioral domain. A similar survey will be used to assess therapist's perception of the success of the HPOT session.

During the HPOT session, the researchers will monitor the heart rate variability of the horse and the rider. Heart rates will be recorded with the Hylofit system (<https://hylofit.com>) worn by the human and horse, respectively. Both horse and rider will wear an electrode strap around the upper thorax. To assess movement coupling between the horse and rider, five tri-axial inertial sensors (OPAL, APDM, Inc, Portland, OR) will be used. The sensors will collect actively synchronized tri-axial accelerometer and gyroscope data at 80 samples per second. One inertial sensor will be placed dorsal at the rider's pelvis, one frontal at the top of the helmet, and one frontal at the top of the sternum. The sensors on the horse will be fixed on the back of the horse on the spine level between T8 and T10 and on the head. Data will be stored on each sensor's internal memory and downloaded following the collection.

Biostatistical Analysis

Specific Aim 1, Hypothesis 1: For the postural sway and social skill measures, as well as the equine stress measures, we will perform a two-way mixed (2x2) ANOVA. We will compare dependent variables between TD children and children with ASD before and after a 6-week HPOT program.

Specific Aim 2, Hypotheses 1, 2: For the coupling measures of heart rate variability and movement, we will perform an independent t-test between the group of children with ASD and the group of TD children at each session. We will also perform a 2x3 mixed way ANOVA to determine how the coupling measures change over time and with intervention.

Specific Aim 3, Hypothesis 1: We will utilize a multivariate regression model to examine the relationship between changes from pre- to post-HPOT session in standing posture, social behavior, and caregiver perception, with the equine temperament and heart rate and movement coupling indices between horse and rider.

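### Does Aim 1 risk mixing an immediate ride effect into the 6-week programme effect by not saying which assessments count as before and after?

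*Combined protocol and SAP*

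**What the plan says.** The document is a short combined protocol and SAP. Its data-collection text gives the timing of the two outcomes: "Standing posture data will be collected pre- and post-HPOT sessions" and "Social play will also be conducted pre- and post-HPOT session". The word session is used there for the ride itself: "The HPOT session will take place within the barn facility", and "During the HPOT session, the researchers will monitor the heart rate variability of the horse and the rider". The same text refers the reader to Figure 1 for a summary of the assessments; that figure is not in the text available here.

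Under Biostatistical Analysis, Specific Aim 1, Hypothesis 1, the model for posture, social skills and equine stress is "we will perform a two-way mixed (2x2) ANOVA", with the comparison described as "We will compare dependent variables between TD children and children with ASD before and after a 6-week HPOT program". Specific Aim 2 has a t-test at each session for the coupling measures and adds "We will also perform a 2x3 mixed way ANOVA to determine how the coupling measures change over time and with intervention". Specific Aim 3 uses "changes from pre- to post-HPOT session in standing posture, social behavior, and caregiver perception".

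No sample size, alpha, effect size, SD or correlation is stated. The point concerns posture and social measures only, because no collection around the ride is described for equine stress.

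**The concern.** The same outcomes seem to be described on two time scales. The data-collection text and Aim 3 speak of change around a session, and a session is a ride. Aim 1 speaks of change across six weeks. If posture and play are measured before and after both the first and the last assessed ride, each child has four candidate values for two cells of the ANOVA, and Aim 1 does not say which two to use.

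The troublesome choice is a natural one. Taken word for word, only the first pre-ride value precedes the whole programme and only the last post-ride value follows all of it. That pair would count a short-lived change in sway or sociability as a programme effect, or let post-ride fatigue hide a real one. The study title names the effectiveness of a 6-week programme, so that is the quantity a reader will want. A reader also could not tell whether Aims 1 and 3 describe the same change.

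**Working it through.** The plan gives no figure to reproduce. The check is algebra on the 2x2 contrast, an illustration of scale, and a comparison of the two possible readings.

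**Algebra.** Let P be the programme effect and R the immediate effect of a ride.

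- First pre-ride to last post-ride: P + R.
- First pre-ride to last pre-ride: P.
- First post-ride to last post-ride: P, if R is the same at both sessions.
- Group x time with the mismatched pair: (P_ASD − P_TD) + (R_ASD − R_TD).

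So R enters the time main effect in full. It enters group x time only through a difference in R between groups.

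**Scale.** All inputs are assumed: P = 0, ride shift d in SD units, n per group, within-child correlation r = 0.5 to 0.7, two-sided 0.05. The change-score SD is sqrt(2(1 − r)), which is 1.000 at r = 0.5 and 0.775 at r = 0.7; df = 2n − 2.

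- Time, both groups shift: noncentrality = d × sqrt(2n) / sqrt(2(1 − r)). For d = 0.3, n = 15: 0.3 × sqrt(30) / 1.000 = 1.643 and 0.3 × sqrt(30) / 0.775 = 2.121.
- Group x time, one group shifts: noncentrality = d × sqrt(n/2) / sqrt(2(1 − r)). For d = 0.3, n = 15: 0.3 × sqrt(7.5) / 1.000 = 0.822 and 0.3 × sqrt(7.5) / 0.775 = 1.061.

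Rejection rates from the noncentral t (r = 0.5 to r = 0.7):

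| n per group | d | Time, both groups shift | Group x time, both shift equally | Group x time, one group shifts |
|---|---|---|---|---|
| 10 | 0.3 | 24.6–37.5% | 5% | 9.7–13.0% |
| 15 | 0.2 | 18.5–27.7% | 5% | 8.3–10.5% |
| 15 | 0.3 | 35.5–53.5% | 5% | 12.5–17.6% |
| 15 | 0.5 | 75.3–92.7% | 5% | 26.2–40.0% |
| 20 | 0.3 | 45.6–66.5% | 5% | 15.2–22.3% |

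With pre-ride values at both ends, or whenever R = 0, both tests stay at 5%.

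**Which reading the text supports.**

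- For the ride-level reading: the session is placed in the barn, heart rate is monitored during it, and Aim 3 takes change across it.
- For the programme-level reading: posture is collected around sessions in the plural, and the assessments are introduced as pre- and post-HPOT without the word session. Aim 1 uses two time levels where Aim 2 uses a three-level factor for measures recorded during rides. That fits coupling recorded on three occasions and posture and play assessed twice.

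If posture and play are assessed only twice, there is nothing to choose between and the 2x2 fits directly. A ride effect would then enter only if the closing assessment directly followed a ride, which no visible sentence says.

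**The case for a change.** The strongest case for a change is that the bias on the mismatched pair is exactly R, whatever the sample size, and that one sentence naming a like-for-like pair would rule it out. Naming the pair in advance would also stop it being picked after results are seen. Even if pre and post are meant at programme level throughout, the session wording in the data-collection text and in Aim 3 would benefit from alignment.

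The algebra stands, and so does the observation that the visible Aim 1 text leaves the two values unnamed. Three things weaken the case for requiring a change.

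- The large rates belong to the time main effect. The comparison Aim 1 states is between children with ASD and TD children, most directly the group x time test, and a shared ride effect cancels there. The visible text also describes no arm without HPOT, so a time main effect could not be credited to the programme alone even with pre-ride values at both ends.
- The obvious remedy, pre-ride values at the first and last sessions, presumes that a pre-ride value exists at the last session. The visible text does not confirm this. Such a value would also precede the final ride, so it is not strictly an after-programme measurement; adopting it could alter the stated contrast.
- Figure 1 is where the assessment timing would be expected. Its absence from the extracted text cannot be held against the plan.

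**Conclusion.** The concern is right that the visible Aim 1 wording does not identify the two assessments, and right about what the mismatched pair would do. It does not show that following the plan gives a wrong result: nothing visible prescribes first pre-ride against last post-ride, and the layout of Aims 1 and 2 is compatible with posture and play being assessed once at each end.

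An analyst holding four values per child would sensibly compare like with like; one holding two has no choice to make. In either case the 2x2 ANOVA serves, and the ASD-versus-TD test is unaffected unless the immediate ride effect differs between groups.

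The possible size, for example 35.5–53.5% rejection for time and 12.5–17.6% for group x time at n = 15, rests wholly on the mismatched pair, an assumed 0.3 SD ride shift (in both groups for the first range, in one group only for the second) and an assumed correlation of 0.5 to 0.7. The documents support none of these inputs. What remains is a minor matter of definition, which the analysis report can settle by naming the assessments used in Aim 1 and saying whether Aim 3's change is across a session or across the programme. No change to the plan is called for.

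### Aim 1 compares non-randomised ASD and TD groups with no age term, so any age difference between the groups can appear as an ASD effect in the between-group results for sway and social skill

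*Combined protocol and SAP*

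**What the plan says.** Under Biostatistical Analysis, Specific Aim 1, Hypothesis 1, the outcomes and the method are given in one sentence: "For the postural sway and social skill measures, as well as the equine stress measures", "we will perform a two-way mixed (2x2) ANOVA". The next sentence defines the comparison: "We will compare dependent variables between TD children and children with ASD before and after a 6-week HPOT program". The two factors are therefore diagnosis group (ASD or TD) and time (before or after). No covariate is named, and the text does not say whether Hypothesis 1 rests on the group main effect, on the contrasts at each time point or on group x time.

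Age appears once, in the data-collection paragraph on social play, where the materials include "similar age-appropriate toys depending upon the age of the child". The supplied text gives no age range, no matching or stratification by age, and no description of how the TD children are chosen.

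**The concern.** A child's diagnosis is not assigned, so nothing in the design makes the two groups alike in age. Age plausibly affects both standing sway and play behaviour in children. For the social measure the link is closer still, because the toys a child is observed with depend on age. If the ASD children were on average younger or older than the TD children, an ANOVA with group and time alone would attribute the age effect to diagnosis.

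At stake is the reading of the group main effect and of the group contrasts at pre and at post. A reported ASD-TD difference could be partly or wholly an age difference, or a true difference could be masked. A larger sample would not help, since it makes the same bias more likely to reach significance.

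**Working it through.** **What can be taken from the documents.** The plan gives no sample size, alpha, SD or age distribution, so it has no figure to reproduce. What follows is an illustration, and all of its inputs are assumptions:

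- children per group n = 10, 15 or 30
- within-group age-outcome correlation r = 0.3 or 0.5
- difference in mean age d = 0.5 or 1 SD
- pre-post correlation of the residual, given age, = 0.7
- two-sided level 5%, outcome SD 1, no true ASD effect

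**Step 1: bias.** The spurious ASD-TD difference is r x d. It runs from 0.3 x 0.5 = 0.15 SD to 0.5 x 1 = 0.50 SD.

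**Step 2: group main effect.** This compares each child's mean of pre and post. The within-group variance of that mean is V = r² + (1 - r²) x (0.7 + 0.3/2) = r² + 0.85 x (1 - r²):

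- r = 0.3: V = 0.09 + 0.7735 = 0.8635
- r = 0.5: V = 0.25 + 0.6375 = 0.8875

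The noncentrality is r x d / sqrt(2V/n), with 2n - 2 degrees of freedom. For example, at n = 15, r = 0.5, d = 1 it is 0.50 / sqrt(2 x 0.8875/15) = 0.50/0.344 = 1.45. The noncentral t distribution then gives these false-positive rates:

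| n per group | r = 0.3, d = 0.5 | r = 0.3, d = 1 | r = 0.5, d = 0.5 | r = 0.5, d = 1 |
|---|---|---|---|---|
| 10 | 6.4% | 10.5% | 8.7% | 20.3% |
| 15 | 7.1% | 13.7% | 10.8% | 28.9% |
| 30 | 9.4% | 23.3% | 17.3% | 52.5% |

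Simulation of the 2x2 design agrees to within about two percentage points. With age as a covariate the simulated rate is about 4-6% in every setting.

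**Step 3: contrasts at pre or at post.** A single measurement has variance 1, so the noncentrality is r x d / sqrt(2/n). At n = 15 and r = 0.5 the rates are 10.1% (d = 0.5) and 26.2% (d = 1).

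**Step 4: group x time.** If age shifts pre and post equally, it cancels from each child's change. Simulated rejection stays at about 5% whatever the age gap. If age also modifies the change, it does not cancel: with an assumed 0.3 SD change per SD of age, n = 20 and d = 1, the rate is about 24%.

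**Step 5: effect of adjustment on the standard error.** Adding age multiplies the residual SD by sqrt(0.85 x (1 - r²)/V), which is 0.946 at r = 0.3 and 0.848 at r = 0.5. Estimating the slope multiplies the standard error by about sqrt(1 + (n x d²/2 + 1)/(2n - 4)).

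- Group main effect, no gap: the product runs from 0.946 x sqrt(1 + 1/16) = 0.976 (n = 10, r = 0.3; simulated 0.972) to 0.848 x sqrt(1 + 1/56) = 0.855 (n = 30, r = 0.5). The fall is about 3% to just over 14%.
- Group main effect, n = 10, r = 0.3, 1 SD gap: 0.946 x sqrt(1 + 6/16) = 1.11 (simulated 1.10), so the interval widens by about 10%.
- Group x time with age x time added, when age does not modify change: there is no residual gain, so only the second factor acts. It is sqrt(1 + 1/56) = 1.009 to sqrt(1 + 1/16) = 1.031 with no gap, and sqrt(1 + 6/16) = 1.173 with a 1 SD gap at n = 10. The standard error rises by about 1-3% and by up to about 17%.

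**The case against.** The strongest reply has four parts.

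- *In a pre/post study of a 6-week programme, the natural target is group x time, and a stable age effect does not bias it.* This stands. A reader might infer that the whole Aim 1 analysis is distorted, and the documents do not support that. However, the plan does not make group x time its only target. It speaks of comparing the two groups before and after, and those contrasts are exposed.
- *Nothing shows that the groups differ in age.* This stands. The toy sentence shows that age varies among children, not between groups. Nor does chance imbalance alone supply the inflation: averaged over chance gaps from a common age distribution, the unadjusted test keeps its 5% level. The rates in the table need a systematic gap arising from who is recruited.
- *Matching may be described elsewhere.* It may. The supplied text has no eligibility or recruitment section, so matching is unstated rather than known to be absent. Even with matched groups, age in the model would sharpen the group main effect if age is related to the outcome.
- *Adjustment does not help everywhere.* Correct. It might seem that adding age and age x time always gains precision. For group x time it costs precision when age does not modify the change.

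None of this removes the gap for the between-group contrasts.

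**Conclusion.** The concern holds for the group main effect and for the group contrasts at pre and at post, for sway and social skill. The plan compares non-randomised groups, states no matching, and leaves out an age variable that it already uses in running the play session. Group x time is at risk only if age modifies the change over the programme.

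The mechanism follows from the design, but its size does not. The false-positive rates depend entirely on the assumed sample size, correlation and age gap, and they vary widely across those assumptions. They should not be read as estimates for this trial. The documents do not support a claim that the groups are imbalanced, or that matching was not done.

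**What to change.** In the Aim 1 paragraph, for sway and social skill:

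- Add centred age as a pre-specified covariate, as a main effect only. With complete pre/post data this leaves the group x time estimate as planned.
- Report the age distribution by group, and say whether the groups were matched on age.
- Give the unadjusted 2x2 ANOVA result alongside.
- Add age x time only in a sensitivity analysis of group x time.

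The text change is a sentence or two and needs no new data collection. The statistical cost is one degree of freedom, an assumed linear age effect, and a wider interval for the group effect if the groups differ strongly in age. The sensitivity analysis carries the group x time standard-error cost worked out above, which is why age x time should stay out of the primary model.

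### No horse term is planned for coupling, equine stress or temperament; if children share horses, the error rates of these tests depend on a horse allocation that the plan does not state.

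*Combined protocol and SAP*

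**What the plan says.** In Biostatistical Analysis, Specific Aim 2, the coupling measures are compared by group: "we will perform an independent t-test between the group of children with ASD and the group of TD children at each session". A longitudinal analysis follows: "We will also perform a 2x3 mixed way ANOVA to determine how the coupling measures change over time and with intervention".

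Specific Aim 1 puts equine stress in the same analysis as the child outcomes: "as well as the equine stress measures, we will perform a two-way mixed (2x2) ANOVA". The contrast is ASD against TD: "We will compare dependent variables between TD children and children with ASD before and after a 6-week HPOT program".

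Specific Aim 3 begins "We will utilize a multivariate regression model to examine the relationship between changes from pre- to post-HPOT session in standing posture" and relates the child changes "with the equine temperament and heart rate and movement coupling indices between horse and rider".

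The paragraph on HPOT-session measurements, just before Biostatistical Analysis, shows that the horse is itself measured: "the researchers will monitor the heart rate variability of the horse and the rider". Inertial sensors are also fixed to the horse. The opening paragraph places the study at one site: "All data collection sessions will take place at the HETRA facility".

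None of these analyses includes a horse factor, a horse random effect or a cluster adjustment. The text does not give the number of horses, how they are assigned to ASD and TD children, whether a child keeps the same horse, how often temperament is rated, or whether the child or the horse is the subject in the equine-stress ANOVA.

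**The concern.** An independent t-test treats each child's value as independent of the others. If two children ride the same horse, part of what is measured is common to both. The consequence depends on how horses line up with group:

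- **Horses separated by group:** a difference between horses enters the group difference, and the test can report it as ASD against TD.
- **Horses balanced across groups:** the horse effect cancels from the group difference but stays in the error term. The test is too cautious and less efficient than a model with horse.
- **Allocation unrelated to group:** the two effects offset on average.

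The same reasoning covers the group main effects in the 2x3 ANOVA (coupling) and, if the child is the subject, the 2x2 ANOVA (equine stress). For the temperament slope, a predictor that takes one value per horse carries only as many independent values as there are horses, however many children are enrolled.

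Without the allocation, a reader cannot tell the direction or size of any error. Postural sway and social skill in Aim 1 are outside this point.

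**Working it through.** **Inputs.** The documents give no sample size, alpha, horse count or ICC, so there is no stated figure to reproduce. Everything below is assumed: two-sided 5%, 8 to 20 children per group, mostly 4 to 10 horses, ICC up to 0.5.

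**Formula for the t-test.** Let n be children per group and m children per horse within a group. Relative to independent data, the variance factor of the group difference is:

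- separated by group: 1 + (m - 1) x ICC
- balanced: 1 - ICC
- what the t-test uses in either case: 1 - ICC x (m - 1)/(n - 1)

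Approximate type I error is 2 x [1 - Φ(1.96 / √(true/used))].

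**Worked case: n = 12, 4 horses.** Separated means 2 horses per group, so m = 6. Balanced means all 4 horses carry both groups, so m = 3.

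| Layout | ICC | True factor | Factor used | Ratio | Error, formula | Error, simulated |
|---|---|---|---|---|---|---|
| Separated | 0.1 | 1 + 5 x 0.1 = 1.50 | 1 - 0.1 x 5/11 = 0.955 | 1.571 | 11.8% | 11.2% |
| Separated | 0.3 | 1 + 5 x 0.3 = 2.50 | 1 - 0.3 x 5/11 = 0.864 | 2.895 | 24.9% | 24.0% |
| Balanced | 0.1 | 0.90 | 1 - 0.1 x 2/11 = 0.982 | 0.917 | 4.1% | 4.1% |
| Balanced | 0.3 | 0.70 | 1 - 0.3 x 2/11 = 0.945 | 0.740 | 2.3% | 2.6% |

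Allocation unrelated to group gave 4.6-5.2% in this setting, and one child per horse gave 4.9%.

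**Simulated t-test error, 15 per group, ICC 0.1 to 0.5.**

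| Layout | 4 horses | 6 horses | 10 horses |
|---|---|---|---|
| Fully separated | 12-41% | 10-29% | 7-18% |
| 75/25 separation | 7-15% | 6.5-12% | 6-10% |

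Balanced layouts gave about 4% at ICC 0.1 and 0.9-1.8% at ICC 0.5. Unrelated allocation gave 4.6-5.5% on average. The realised layout still matters there: the 10th to 90th percentile of error across layouts was 4.1-5.9% at ICC 0.1 and 2.0-9.0% at ICC 0.5.

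**ANOVA terms (12 per group, 4 horses, two or three time points).** The group main effect had 23-30% error when separated and 2.2-2.9% when balanced. The group-by-time term was 4.8-5.2% with a constant horse effect. When the horse effect varied over time it was 18-37% separated and 1.8-3.4% balanced.

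**Temperament slope (24 children, one rating per horse).** With 4 horses, error was 7.9%, 11.0%, 17.7% and 23.4% at ICC 0.05, 0.1, 0.2 and 0.3. Over the same ICC range it was 6.8-16.8% with 6 horses and 5.5-8.7% with 12. At ICC 0 it was about 5%. If ratings vary by child but 40-70% of their variance lies between horses, error was still 6-18% at ICC 0.1 to 0.3. These are single-outcome slopes; the multivariate model itself was not simulated.

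**Does the remedy work?**

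- With 15 per group and ICC 0.1 to 0.5, a horse random intercept with Wald z inference left 6.1-16.6% error for nested horses. Satterthwaite gave 4.0-7.1% and Kenward-Roger 0.1-4.9%. At ICC 0.1 the horse variance was estimated as zero in 34-42% of runs.
- With 12 per group and ICC 0.1 or 0.3, a test on horse means in nested layouts gave 4.9-5.0% error.
- With 4 nested horses, 15 per group and a 0.8 SD difference, power was 10-18% on horse means against 4-7% with Kenward-Roger (ICC 0.1 to 0.5).

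**The case against.** The strongest reply is that no defect has been shown. The harm needs children to share horses, a horse ICC above zero and, for inflation, horses aligned with group. None of these is documented. A single facility makes sharing plausible but says nothing about horse numbers or allocation. This stands, and the point is therefore conditional.

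Four further objections also stand:

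- **Unit of the equine-stress ANOVA.** If horses are separated by group and the horse is the subject, the horse is already the error unit and there is no inflation.
- **Balanced horses.** A reader might infer that real group differences would be lost. The t-test's power at 0.8 SD (15 per group) stays at 56-65%, against 56% without clustering. The loss is only relative to a model with horse, about 4 points at ICC 0.1.
- **Temperament.** Sharing and one rating per horse are not enough; change scores must also cluster by horse, and that clustering may be small. Figure 1, which is not reproduced in the text available for review, may say when temperament is rated.
- **Remedy.** Kenward-Roger does poorly with 4 to 6 nested horses, and a horse intercept alone does not deal with horse effects that change over time. The fix provides for both.

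The objection does not remove the case for acting. The plan measures the horse and uses it as a predictor, so the unit and the allocation need stating. If horse ID is not recorded, the analysis may not be repairable later.

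**Conclusion.** The point holds conditionally. The plan has no horse term and does not state horse numbers, allocation or the unit for equine stress.

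If children share horses, horse ICC is above zero and the child is the unit, the per-session coupling t-tests and the group main effects are:

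- anti-conservative when horses are wholly or partly separated by group (about 7-40% t-test error if fully separated);
- conservative and less efficient when balanced (about 1-4%);
- near nominal on average when allocation is unrelated to group (about 5%).

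These figures assume 15 per group, 4 to 10 horses and ICC 0.1 to 0.5. The top of the range needs full separation, 4 horses and ICC 0.5 together.

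The temperament slope is anti-conservative if temperament is wholly or largely a horse-level value and child change scores cluster by horse. With no clustering there is no error, and at ICC 0.05 it is small (6-8% with two coupling covariates in the model).

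A reader might infer that the planned group tests are invalid as they stand, or that sharing alone makes them so. The documents support neither. Nor do they support a claim against the group-by-time terms, which are unaffected if each child keeps one horse and its effect is constant.

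The change is worth making as an inexpensive improvement. Confidence is medium, because every size rests on assumed inputs.

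**What to change.** 1. Record horse ID at every session. State the number of horses, their allocation by group, whether a child keeps the same horse, and the subject unit of the equine-stress ANOVA.
2. Where horses carry more than one child, fit the coupling and equine-stress models with a horse random intercept. Cross it with child if children change horses, and add a horse-by-time term if the data support it. Use small-sample inference (Kenward-Roger, or Satterthwaite if that is not available) and take the per-session group contrasts from this model in place of the independent t-tests.
3. If horses are nested in group and few (about 6 or fewer), test group on horse means or report the contrast descriptively, stating that it is confounded with horse.
4. In Aim 3, add a horse random intercept or use horse-level inference whenever horses are shared, not only if temperament is rated once per horse.
5. Omit the horse term if each child has a unique horse or the horse is already the unit of analysis.

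**Cost.** The change needs one identifier per session, a model term and some SAP wording. The statistical price is about (horses - 2) degrees of freedom for group contrasts with nested horses and for the temperament slope: 2 with 4 horses, 8 with 10. With nested horses, 15 per group and a 0.8 SD difference, Kenward-Roger power is 28-38% with 10 horses and 16-24% with 6.

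Elsewhere the term costs little or helps. With balanced horses, power goes from 56-57% to 60-61% at ICC 0.1 and from 59-60% to 70-72% at ICC 0.3. With unrelated allocation, it goes from 56-57% to 54-57% and from 57-61% to 62-65%.

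### Both mixed ANOVAs, as conventionally fitted, drop a child who lacks one analysed occasion for an outcome, and the plan makes no provision for incomplete data; a likelihood-based mixed model would use all observed occasions

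*Combined protocol and SAP*

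**What the plan says.** All the relevant analysis text is in the Biostatistical Analysis section of the combined protocol and SAP.

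- **Aim 1** (postural sway, social skill, equine stress): "we will perform a two-way mixed (2x2) ANOVA". The contrast is "We will compare dependent variables between TD children and children with ASD before and after a 6-week HPOT program", so there are two analysed occasions per child and outcome.
- **Aim 2** (heart rate variability and movement coupling): "we will perform an independent t-test between the group of children with ASD and the group of TD children at each session", followed by "We will also perform a 2x3 mixed way ANOVA to determine how the coupling measures change over time and with intervention". The three levels of the 2x3 design are not named.

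Neither this section nor the data-collection text before it gives an analysis population, a minimum amount of usable data, a deletion rule, imputation or a mixed model.

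The data-collection text shows where values could be lost. For posture, "children will be asked to stand as still as possible for 20 s with their arms at their sides and facing a bare wall". For heart rate, "Both horse and rider will wear an electrode strap around the upper thorax". For movement, "five tri-axial inertial sensors (OPAL, APDM, Inc, Portland, OR) will be used", three of them on the child and two on the horse.

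**The concern.** A conventional (split-plot) mixed ANOVA works on complete rows. If a child has a usable value on one analysed occasion but not on another, the observed value is discarded together with the missing one. Naming this method therefore settles how incomplete data will be treated unless the plan says otherwise, and it does not. A paragraph on missing data that kept the ANOVA would not bring these children back.

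Incomplete rows are foreseeable from the measurements listed, and a coupling index needs usable signals from both child and horse. Two things are at stake:

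- **Precision.** Data already collected are thrown away.
- **Bias.** If the children who drop out differ at baseline, the completers' mean change is shifted by regression to the mean. If this happens more in one group than in the other, the difference enters the group x time interaction.

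**Working it through.** The plan states no figure to reproduce: no sample size, variance, correlation or loss rate. Everything below rests on assumed inputs, shown as ranges. The number of occasions k comes from the plan: 2 for Aim 1, and 3 for Aim 2 if the unnamed levels are time points.

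**1. Share of complete rows.** With independent loss m per occasion the share is (1 − m)^k.

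| m | k = 2 | k = 3 |
|---|---|---|
| 10% | 0.9² = 81% | 0.9³ = 72.9% |
| 20% | 0.8² = 64% | 0.8³ = 51.2% |

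If instead the same children are lost on every occasion, 90% and 80% of rows stay complete whatever k is.

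**2. Bias when loss depends on the observed baseline.** Assume SD 1, no true change, and a post value missing with logit slope 1 per SD of baseline and 25% missing overall. By numerical integration this needs an intercept of about −1.315, and completers' mean baseline then lies 0.213 SD below the group mean. Their mean change is shifted by (1 − ρ) × 0.213, where ρ is the pre-post correlation:

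- ρ = 0.5: 0.5 × 0.213 = 0.107 SD
- ρ = 0.7: 0.3 × 0.213 = 0.064 SD

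The likelihood estimate on all observed data has no such shift under this mechanism.

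**3. Comparison under three loss mechanisms.** Large-sample simulation: SD 1, correlation 0.5, true change 0.50, first occasion always observed, about 25% to 30% loss at each later occasion.

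| Loss depends on | Complete cases, k = 2 / k = 3 | Mixed model, k = 2 / k = 3 |
|---|---|---|
| nothing (MCAR) | 0.50 / 0.50 | 0.50 / 0.50 |
| observed first value (MAR) | 0.38 / 0.30 | 0.50 / 0.51 |
| the unobserved value itself (MNAR) | 0.62 / 0.62 | 0.69 / 0.68 |

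**4. Precision.** Take independent random loss m on every occasion, q = 1 − m, and compound symmetry with correlation ρ. The large-sample variance of the first-to-last change, mixed model relative to complete cases, is:

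- k = 2: q / [q + m(1 − ρ)]
- k = 3: q² / [q² + qm(2 + ρ)/(1 + ρ) + m²(1 − ρ)]

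| m | ρ | k = 2 | k = 3 |
|---|---|---|---|
| 10% | 0.5 | 0.947 | 0.839 |
| 10% | 0.7 | 0.968 | 0.847 |
| 20% | 0.5 | 0.889 | 0.691 |
| 20% | 0.7 | 0.930 | 0.706 |

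For example, with k = 3, m = 20% and ρ = 0.5: 0.64 / (0.64 + 0.16 × 2.5/1.5 + 0.04 × 0.5) = 0.64/0.927 = 0.691. The variance therefore falls by about 3% to 11% for two occasions and 15% to 31% for three.

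**The case against.** Much of the case on the other side stands, and it limits the point.

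- **Complete-case analysis is inferred.** The plan nowhere says that only complete children are analysed. It follows from how the named method is normally fitted. That is enough to recommend a better method, but not to report a stated deletion rule.
- **A reader might infer that any missed or unusable session removes the child from the study.** The documents do not support this. Only an analysed occasion counts, and only for the outcome concerned: an intermediate session missed during the programme removes nobody from the 2x2, and a strap failure does not touch sway. The Aim 2 t-tests at each session keep every child measured that day. For posture, "Children will perform 3-5 trials of standing", so one bad trial need not lose the assessment. How trials are reduced is not stated, but averaging them is legitimate, and a trial-level model is not needed.
- **A reader might infer that a mixed model avoids selecting the most compliant children with ASD.** It does not. Its validity rests on missing at random. Distress, strap refusal or inability to stand still may depend on the child's unobserved state that day. Under such a mechanism the simulation left both methods biased, the mixed model slightly more. No model recovers children who were never measured.
- **Higher loss in the ASD group is an assumption.** The documents give no figure for it.
- **The bias is small beside the likely standard error.** Assume 10 to 30 children per group and 25% loss in one group only. The group x time standard error is √{2(1 − ρ)[1/n + 1/(0.75n)]}. That is 0.48 SD for n = 10, ρ = 0.5 and 0.22 SD for n = 30, ρ = 0.7. The bias is then about 0.17 to 0.38 of a standard error across these settings (0.064/0.374 to 0.107/0.279).

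None of this favours the ANOVA under MCAR or MAR, where it is never better than the mixed model in large samples.

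**Conclusion.** The concern holds in a limited form. The plan commits to two analyses that, as conventionally fitted, discard the observed data of any child lacking an analysed occasion, and it provides nothing else for incomplete data. A likelihood-based mixed model uses those data and is valid under a weaker assumption.

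For the 2x2 the argument rests mainly on bias under missing at random, because the precision gain is modest. For the 2x3 the precision gain is material, provided the three levels are time points. All sizes depend on assumed loss rates, correlations and mechanisms, and the fall in complete rows is smaller if the same children are lost each time. The change is worth making before analysis. The documents do not show that the results will be seriously biased.

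**What to change.** In the Biostatistical Analysis section, Aims 1 and 2:

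1. Replace both mixed ANOVAs with a linear mixed model fitted by REML to all observed occasions, with fixed effects for group, time and group x time. Keep the group x time and within-ASD contrasts, and use Kenward-Roger or Satterthwaite degrees of freedom.
2. Specify **either** an unstructured within-child covariance **or**, if the sample is small, a random intercept (compound symmetry), but not both. With one value per occasion the two together are not identifiable: two occasions give 3 covariance moments for 3 + 1 = 4 parameters, and three occasions give 6 for 6 + 1 = 7.
3. Name the three levels of the 2x3 analysis and the minimum usable data that make an occasion count as observed.
4. State that validity rests on missing at random. Report missingness and its reasons by group, and add a sensitivity analysis for data missing not at random.

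The cost is SAP wording and a different procedure in the same software. With complete, balanced data the simplest form gives the same tests as the ANOVA. The downside is that the covariance may have to be simplified when the sample is small.
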